#### IV. Participants:

Describe the study participants and the population from which they will be drawn. Specify the inclusion and exclusion criteria. If you plan to include children, note their ages and whether you will include children in foster care. Note if the participants are particularly vulnerable in terms of cognitive limitations, education, legal migration status, incarceration, poverty, or some combination of factors.

- **Inclusion Criteria:**

##### Stage 1A:

Data will be collected from three participant types in Stage 1A.

(1) PLWH who have a history of alcohol use while on ART.

- 18 years of age or older
- HIV-infected
- Currently a patient receiving care in one of the study HIV clinics
- Current or previous use of alcohol while on ART
- Provides informed consent

(2) Health workers/clinic staff at our two study clinics

- 18 years of age or older

- Currently works in one of the study HIV clinics in a position that will be relevant for CETA integration
  - Provides informed consent
- (3) Policy and program-level stakeholders (e.g., Ministry of Health officials)
- 18 years of age or older
  - Works for MoH or is a key informant in the Zambia HIV Health system or is a key informant in the area of alcohol policy and treatment.
  - Provides informed consent

### Stage 1B:

Study participants will be PLWH who are currently receiving care at one of the two study clinics. Participants will be recruited by their regular care providers (i.e., peer educators, counselors, nurses, physicians) and referred to study staff if they are interested. We anticipate enrolling a total of 320 participants, all of whom have hazardous alcohol use. 50% of them will be lower-risk drinkers who do not have moderate-to-severe alcohol use disorders (AUD) or mental health comorbidity. These participants will be part of the 'Cohort Study'. These will not be randomized. The other 50% will be high-risk drinks due to having either moderate-to-severe AUD or mental health comorbidities, or both. This second group will be randomized into the RCT Study. The minimum age of research subjects will be 18. All subjects will be recruited from our two study clinics. Eligibility will be assessed via audio computer assisted self-interviewing (ACASI).

*Initial* inclusion criteria for overall enrollment (into either the Cohort or RCT study) will be:

- HIV positive
- Receiving HIV treatment services at one of the two study clinics
- Current hazardous alcohol use, defined as an AUDIT score of  $\geq 8$  for men and  $\geq 4$  for women
- Provides informed consent

*Secondary* inclusion for enrollment into the RCT will be:

- AUDIT scores that indicate a moderate-to-severe AUD ( $\geq 12$  for women;  $\geq 16$  among men)
- AND/OR: meeting validated symptom criteria for depression ( $\geq 16$  on CES-D), trauma/anxiety ( $\geq 2.5$  on HTQ), and/or substance use ( $\geq 27$  for any non-tobacco/alcohol substance on ASSIST)

Participants who meet initial inclusion criteria AND secondary inclusion criteria will be eligible for the RCT. Participants who meet initial inclusion criteria but NOT secondary inclusion criteria will be eligible for the Cohort study.

- **Exclusion Criteria:**

Stage 1A: No formal exclusion criteria.

Stage 1B: Study exclusion criteria for Stage 1B (applies to the Cohort study and the RCT) will be:

- HIV negative

- Not receiving care at one of the study clinics
- Currently psychotic or on an unstable psychiatric drug regimen
- Actively suicidal: Suicide attempt or suicidal ideation with intent or plan, or self-harm in the past month.
- Unable to provide informed consent

**NOTE:** If you are recruiting participants or receiving, accessing, or using data from a U.S. health care provider, HIPAA review is likely to be required. If you plan to bring identifiable health information from a foreign country to a U.S. covered entity (e.g., lab at the Hopkins SOM), HIPAA may be triggered. Check “yes” to the HIPAA question in the PHIRST application.

## V. **Study Procedures:**

In this section, provide details of your procedures, particularly as they relate to human subjects. If this is a multi-center study, make the role of JHSPH clear. If the JHSPH will serve as **data coordinating center**, indicate in the sections below which procedures JHSPH will not be performing. Additional information regarding data coordinating centers is requested in a later section. If your study will develop in phases, address each item below by phase.

### A. **Recruitment Process:**

1. Describe how you will identify, approach, and inform potential participants about your study. Include details about who will perform these activities and what their qualifications are.

Before any data collection begins, community meetings will take place at each site in order to explain the procedures of the study, the risk and benefits, the confidentiality of results, and to allow for any questions. Based on our prior experience using this approach in Zambia, which has featured good relationships with the local population, we do not anticipate difficulties in obtaining community approval.

- Stage 1A: CETA Adaptation

PLWH study participants for Stage 1A will be recruited from their regular care providers at the study HIV clinics in Lusaka. Care providers will be asked to inform their adult patients with a history of alcohol use while on ART about the presence of the qualitative study using a recruitment script (included with this IRB application). Interested participants will be referred to our on-site study assessor. The assessor will explain the study in full and obtain informed consent if the participant is interested. The assessor will obtain contact information from the participant to schedule the focus group discussion, which will happen at a later date. This method will ensure that only patients who express interest in the study to their usual care provider will have any contact with research staff.

Health worker and policy level participants will be contacted by a study assessor and informed about the qualitative study. Due to our team’s ongoing collaborative work with the study clinics and the Ministry of Health, we have an existing sampling frame of stakeholders who we will ask to participate in focus group discussions and key informant interviews. Our study team will contact these stakeholders about participation and explain the purpose of the study. If potential participants are interested, the assessor will obtain informed consent and participant contact details to set up the focus group discussion or key informant interview.

- Stage 1B: Pilot RCT of CETA

Study participants for the pilot RCT will be recruited from two HIV clinics in Lusaka. Participants will be recruited from the general HIV+ patient population at these clinics. While receiving regular care at these HIV clinics, clients will be informed of the pilot RCT by a care provider, which may be their physician, nurse, a

peer educator, or a counselor. We will provide training to these care providers in the background of the study and human subjects research. We will provide them with a recruitment script (included in this IRB application) to ensure that their description of the study is consistent. Staff will emphasize at the outset that participation in the pilot RCT will not affect whether or not the participant receives HIV care as usual. Interested participants will be referred to our on-site study assessor, who will be stationed in a private room within the clinic.

All recruitment activities will be conducted by HIV care providers working in the study clinics and/or personnel of the study implementing organization, Centre for Infectious Disease Research in Zambia (CIDRZ). All personnel working on the study will receive training on study procedures, human subjects research, and research ethics. They will also have certification in human subjects research from relevant NIH modules.

2. Address any privacy issues associated with recruitment. If recruitment itself may put potential participants at risk (if study topic is sensitive, or study population may be stigmatized), explain how you will minimize these risks.

Recruitment for PLWH (both Stage 1A and Stage 1B) will be conducted by physicians, nurses, peer educators, and counselors who provide them with regular HIV care. These providers will identify PLWH under their care who they think would meet inclusion criteria for the study. This conversation will take place in private and include only the provider and the potential participant, and will be facilitated by a standardized recruitment script. Only if the potential participant agrees to hear more about the study will the provider contact and invite research staff to fully explain the study and obtain informed consent. Therefore, potential participants will have no contact with research staff unless they express an interest in hearing more about the study. Potential participants will be counseled that they can refuse to participate in the study and still receive HIV care at the treatment site. Providers will be highly trained and will receive specific training in human subjects research.

Provider, staff, and policy-level participants for Stage 1A are employees currently working in clinics or relevant programmatic or MoH offices. All potential participants will be contacted by a study assessor who will explain the purpose of the study. If the potential participant is interested in participating, the assessor will set up a time to obtain informed consent and schedule the subsequent focus group or interview. The assessor will additionally counsel potential participants that their participation is completely voluntary, and that whether or not they participate, and regardless of the data they provide during the FGD/KII, their position with MoH or CIDRZ will not be impacted in any way. Senior MoH and CIDRZ officials will not have access to individual FGD/KII data and all data provided from participants will be de-identified and only presented in aggregate to maintain confidentiality of participants.

## **B. Consent Process:**

1. Describe the following details about obtaining informed consent from study participants. If a screening process precedes study enrollment, also describe the consent for screening.

### **A. Who will obtain informed consent, and their qualifications:**

All informed consent activities for all participant types and research phases will be obtained by our trained CIDRZ study assessors. The assessors will be highly trained in human subjects and responsible conduct of research and will have the appropriate certifications (e.g., NIH).

### **B. How, where, and when the consent discussion(s) will occur:**

Consent for participants in Stage 1A will be done in a private room within the HIV clinic or office building where the participant works.

Informed consent from PLWH in Stage 1B will be obtained within a private room within the HIV clinic. This will be done after the patient has been referred to our on-site study assessor by one of their care providers following the recruitment process. Consent will first be obtained for screening. If the participant is eligible following screening, the assessor will then obtain informed consent for the remaining study activities. The second informed consent will be specific to either the cohort or trial study, whichever the participant screened eligible for.

For all consent activities with all participant types, the following information about the study will be discussed:

- Purpose;
- Locations where research will be conducted;
- Points of assessment and the types of questions that will be asked;
- Random assignment to treatments;
- Description of each treatment;
- How privacy will be protected;
- Incentives for research visits and schedule;
- Potential risks;
- Potential benefits;
- The circumstances in which mandated reporting will be required; and
- The participant's rights.

The consent forms will be available in English and two common Zambian languages and consent will occur in the language (among the 3) chosen by the participant. If the participant is not literate in one of the 3 languages, an independent witness (either family member, friend, or clinic staff not working on the study) who is literate in the chosen language will be present and will co-sign the consent. Study procedures will allow for potential participants to take time to make a decision about whether or not to participate and a follow-up appointment within 48 hours of the initial meeting can be scheduled, if desired. The participants will be encouraged to ask questions throughout the consent process and also throughout their entire participation in the study.

C. The process you will use to determine whether a potential participant meets eligibility criteria:

1. Screening for eligibility into the overall study. Participants will provide informed consent for the screening activity. They will then complete a screener that consists of demographic information and the Alcohol Use Disorders Identification Test administered via the audio computer assisted self-interviewing (ACASI). Eligibility criteria for this stage are:

- HIV positive
- Receiving HIV treatment services at one of the two study clinics
- Current hazardous alcohol use, defined as an AUDIT score of  $\geq 8$  for men and  $\geq 4$  for women

Following the ACASI screener, the ACASI system will alert the assessor if the participant is eligible or not. If not eligible, the participant will exit the study. If eligible, the participant will conduct the secondary screening to determine whether they will be part of the cohort or the RCT. The additional screening questions will also be administered via ACASI. Participants will be enrolled into the cohort study unless one or more of the following conditions are met:

- AUDIT scores that indicate a moderate-to-severe AUD ( $\geq 12$  for women;  $\geq 16$  among men)
- AND/OR: meeting validated symptom criteria for depression ( $\geq 16$  on CES-D), trauma/anxiety ( $\geq 2.5$  on HTQ), and/or substance use ( $\geq 27$  for any non-tobacco/alcohol substance on ASSIST)

If any of these conditions are met, the participant will be eligible for and enrolled into the RCT.

Cohort study participants (i.e., lower risk participants) will not be randomized. They will receive the brief alcohol intervention and we will conduct a 6 month post-baseline assessment. The purpose of including them in the study is to gain some preliminary data on whether the brief intervention may be helpful in reducing alcohol consumption among these participants that have a lower level alcohol use problem and no significant mental health or other substance use comorbidities. They are not formally included in the RCT because we did not have the resources to do so in this pilot grant.

RCT participants (i.e., higher risk participants) will be randomized to receive either the brief intervention alone or the brief intervention + CETA. Similar to the cohort participants, we will conduct a 6 month post-baseline assessment among all RCT participants. The purpose of the RCT is to assess whether the BI

alone is effective or whether a more substantial intervention (BI +CETA) is necessary for these higher risk participants.

D. Whether you will obtain a signature from the participant or will use an oral consent process:

As with previous studies conducted among HIV-populations by CIDRZ, we will obtain a signature from the participant.

E. Whether you will obtain a legally authorized representative's signature for adults lacking capacity:

We will not include adults who lack capacity to provide consent in the study.

F. If children are included in the study, if and how you will obtain assent from them:

N/A

G. If children are included in the study, how you will obtain permission for them to participate from their parent, legal guardian, or other legal authority (if child is in foster care or under government supervision):

N/A

H. If you are seeking a waiver of informed consent or assent, the justification for this request:

We are not seeking a waiver.

I. Whether you will include a witness to the consent process and why:

J. If a person is not literate, we will ask them to choose 1 of the 3 languages (English, Bemba, Nyanja) and we will conduct consent orally in that language with a witness present who is literate in that language. Witness cannot be someone employed by the study. After consent the witness will sign the form if the participant agrees.

K. If the language is unwritten, explain how you will communicate accurate information to potential participants and whether you will use props or audio materials:

N/A

2. Identify the countries where the research will take place, and the languages that will be used for the consent process.

Country	Consent Document(s) (Adult Consent, Parental Permission, Youth Assent, etc.)	Languages
Zambia	Stage 1A Qualitative consent Stage 1B Screening consent Stage 1B Cohort consent Stage 1B RCT consent	English, Nyanja, Bemba English, Nyanja, Bemba English, Nyanja, Bemba English, Nyanja, Bemba

a. **Study Implementation:**

1. Describe the procedures that participants will undergo. If complex, insert a table below to help the reviewer navigate.

**Stage 1A: Adaptation of CETA for use in HIV settings**

There will be two key adaptations of the CETA intervention: (1) integration of CETA within regular HIV care; and (2) modification/tailoring of CETA for use with PLWH. The output of Stage 1A is an adapted CETA protocol and standard operating procedure that will be piloted in Stage 1B.

Integration of CETA within HIV care services. We will explore perceived barriers and facilitators of CETA integration within HIV care to inform the protocol. As a preliminary step, we will review the most recent HIV care protocols in our two study clinics to identify possible integration points. We will conduct a series of focus group discussions (FGDs) and key informant interviews (KIIs) with stakeholders on implementation factors.

Stage 1A Participants and Procedures.

Three levels of stakeholders will be convened for this phase:

- ***PLWH who are 18+ years of age and have a documented history of drinking while on ART (4 FGDs; N=5-8 participants per FGD; 50% female)*** will be referred to this qualitative study by care providers in the two study clinics. Discussions will build on our previous qualitative study that explored motivations to drink and abstain among HIV-infected individuals taking ART. In FGDs, a facilitator will introduce the concept of CETA using vignettes, which are an effective tool to engage participants and elicit responses on barriers and facilitators to HIV programs in SSA. As the PLWH have not experienced cognitive behavioral therapy before, vignettes that illustrate CETA being used will be developed in collaboration with existing CETA counselors in Zambia and based on our initial review of the HIV care protocols. They will describe hypothetical CETA sessions and facilitators will probe for feedback from participants on perceived acceptability, appropriateness, and feasibility of CETA using an interview guide (included in this IRB application).
- ***Health workers at HIV clinics (4 FGDs; N=5-8 participants per FGD)*** will also be invited to participate in FGDs. Through our previous studies in these clinics, we already have a sampling frame of providers and staff who will be essential for CETA integration. Additional participants will be recruited through a snowball sampling approach. Similar to the PLWH FGDs, a facilitator will introduce the concept of CETA using vignettes. Discussions will focus on acceptability, appropriateness, and feasibility of delivering CETA within the clinics with an emphasis on logistical hurdles to integration.
- ***Policy- and program-level stakeholders (10-15 KIIs)*** will be recruited with the assistance of [name], a longtime collaborator of our team, senior-level MoH official, and Significant Contributor on this study. These will include MoH officials and key informants in the HIV health system, such as clinic in-charges, district and national coordinators, clinical care specialists, and community advisors to the Zambian ART program. These interviews will inform adoption, integration, and sustainability from a policy perspective.

Stage 1A: Data Collection and Analysis. All qualitative research activities will be audio recorded and transcribed (and translated to English when necessary) and FGDs will include both a facilitator and a note taker. Recordings and notes from the FGDs and KIIs will be analyzed by coding emergent themes using grounded theory, an inductive approach to explore similarities and differences of perceptions to barriers and facilitators for CETA integration across study participants and both clinics. Coding will be done using an *in vivo* method to explore these emergent themes. Results will be used to generate a draft pilot protocol for CETA provision within the HIV clinics. The protocol will be circulated to stakeholders with a chance for review and comment before finalization.

### Stage 1B: Piloting of CETA referral and treatment in HIV clinics.

[figure not shown]
Stage 1B of the study will be a pilot RCT of CETA delivery in HIV clinics. Our hypothesis is that BI+CETA will be more effective than BI alone at treating severe AUD, mental health, and substance use problems. As such, the two populations targeted for this pilot RCT are those that are 'higher risk', namely: (1) PLWH with hazardous drinking and comorbidities; and (2) PLWH with moderate-to-severe AUD (with or without comorbidities). BI alone is currently the standard of care and only alcohol treatment in Zambia HIV clinics and therefore an appropriate comparison to BI+CETA. Participants in these two groups will be randomized 1:1, stratified by sex, to receive BI+CETA or BI alone. Alcohol, substance use, and mental health outcomes will be assessed at baseline and 6-months post-baseline. Retention on ART and HIV viral suppression will also be assessed at baseline and 6-months post-baseline. These HIV outcomes will be assessed as part of usual HIV care. We will also systematically capture data on intervention uptake, attendance, and completion, clinical monitoring, and implementation factors.

Although our focus is on the feasibility of delivering a higher intensity and potentially more effective therapy (i.e., CETA) for individuals at higher risk, we will also provide BI alone for PLWH who report hazardous alcohol use *without* comorbidities and do not meet criteria for a moderate-to-severe AUD (individuals at 'lower risk', referred to as 'cohort' participants in the consent form) and evaluate their outcomes to lay broad foundation for a stepped care intervention in the future. That is, in a real-world program, these are PLWH who would be initially targeted by BI alone. Although enrolling these participants into an RCT is beyond the scope of this study, we will collect pre/post data on the same outcomes as the pilot RCT participants to estimate within group effects of the BI alone for these lower risk drinking problems.

Baseline data collection. The baseline assessment will be conducted via ACASI. The participant will first complete the Alcohol Use Disorders Identification Test (AUDIT) to assess eligibility into the study. The ACASI will automatically alert the assessor if the participant is eligible based on the hazardous alcohol use criteria. If eligible, the participant will complete the remaining measures: (1) Center for Epidemiological Studies-Depression Scale (CES-D); (2) Harvard Trauma Questionnaire (HTQ); and (3) the Alcohol, Smoking, and Substance Involvement Screening Test (ASSIST). All of these measures have previously been translated and used by our team in Zambia and the AUDIT, CES-D, and ASSIST measures have been formally validated. A research assistant will be available if there are any challenges with the ACASI. Additionally, we will use HIV clinic files to extract HIV-related data. These data are captured as part of HIV routine care in Zambia and include: (1) ART initiation date, (2) hepatitis B surface antigen, (3) most recent CD4+ count, (4) cumulative and past 6-month ART retention, defined by medication possession ratio (MPR; an objective pharmacy record metric that we have used previously) and (5) plasma HIV viral load (measured at CIDRZ Central laboratory using the Roche COBAS/Ampliprep platform).

Secondary eligibility criteria for the RCT. Following completion of the baseline assessment, ACASI will automatically alert the assessor if the participant is eligible for the pilot RCT via a built-in algorithm. Criteria for the RCT will be (a) AUDIT scores that indicate a moderate-to-severe AUD ( $\geq 12$  for women;  $\geq 16$  among men) and/or (b) meeting validated symptom criteria for depression ( $\geq 16$  on CES-D), trauma/anxiety ( $\geq 2.5$  on HTQ), and/or substance use ( $\geq 27$  for any non-tobacco substance on ASSIST).

Randomization. Participants eligible for the pilot RCT will be randomized 1:1, stratified by sex, to receive the BI alone or BI+CETA. Participants who are NOT eligible for the pilot RCT will be provided with a BI but will not be randomized.

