number of PLWH participants in Stage 1A will be n=32. Additionally, we will conduct 4 FGDs with health workers at our study clinics. These FGDs will also have a maximum number of 8 participants per group, thus the maximum number of healthcare worker participants will be n=32. Finally, we will conduct up to 16 key informant interviews with policy officials and relevant program leaders.

Stage 1B: This stage will enroll n=320 participant who have hazardous alcohol use: n=160 will formally be enrolled in the RCT (participants who meet criteria for a moderate-to-severe AUD or have hazardous alcohol use plus comorbidities) and n=160 who will not be enrolled in the RCT but will receive the BI and will be tracked for follow-up in a cohort study (participants with hazardous use but do not have a moderate-to-severe AUD and have no comorbidities).

The primary endpoint of the pilot RCT is the difference in change in AUDIT score from baseline to 6-month follow-up between BI+CETA and BI alone (see assessments section below). We believe that an effect size of CETA  $\geq 0.5$  would be clinically significant and justify further investigation in a subsequent latter Stage trial. Further assuming  $\alpha=0.05$  and  $\beta=80\%$ , we will require a total sample size of 128 (n=64 per arm). To account for possible loss-to-follow-up/drop-out of 20% based on our previous studies with HIV-affected populations in Zambia, we will inflate the sample size to 160 (n=80 per arm). Based on Preliminary Studies, we anticipate that 20% of female and 40% of male patients at the study sites will report hazardous drinking and that 50% of hazardous drinkers will qualify for the RCT. Therefore, we expect to enroll n=320 hazardous drinkers to reach the RCT target sample size. There is no sample size calculation for cohort study participant; however, the anticipated sample of n=160 should be sufficient to detect even a small within-group change in outcomes after receipt of BI.

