Follow-up assessments. Alcohol and comorbidities will be assessed in all participants at 6 months (i.e., endline) after baseline. The ACASI questionnaire that was used at baseline will again be administered at this follow-up visit (i.e., the questionnaire at this visit is the same as at baseline). In addition to ACASI assessments, we will confirm self-reports of alcohol abstinence on the AUDIT by conducting a urine-based rapid alcohol biomarker test, ethyl glucuronide (uEtG). Finally, at the 6-month post-assessment, which coincides with a regularly scheduled clinic visit, we will extract relevant information from the client's HIV clinical record (this will be the same information that is collected at baseline), including: , (1) hepatitis B surface antigen, (2) most recent CD4+ count, (4) cumulative and past 6-month ART retention, defined by medication possession ratio (MPR; an objective pharmacy record metric that we have used previously) and (4) plasma HIV viral load (measured at CIDRZ Central laboratory using the Roche COBAS/Ampliprep platform). We will not collect any additional biospecimens for purposes of the study—all HIV-related data will be captured via chart extraction. To supplement retention data captured through MPR measurement, we will also assess visit adherence, the percentage of assigned pharmacy and clinical visits that were made (coming to clinic within 3 days).

Implementation data collection. We will conduct a mixed methods process evaluation with stakeholders involved in the CETA referral and treatment process, including follow-up FGDs and KIIs with participants from Stage 1A and CETA counselors. We will also conduct mixed methods interviews with approximately N=30 PLWH who participated in the Stage 1B pilot RCT. This will include a purposeful sample of PLWH from a range of ages and both sexes who did and did not complete the BI and CETA. Implementation factors to be explored will include: acceptability, appropriateness, reach, cost, feasibility, and sustainability and will explore the attitudes, thoughts, feelings, and barriers and facilitators related to implementation. Interviews will include an in-depth interview component and JHU quantitative implementation measures.

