*Analysis of CETA clinical monitoring data.* We will conduct longitudinal data analysis with CMF and TLFB daily estimates of drinking during CETA. Exploratory analysis will examine trajectories of weekly symptom change based on CMF score and number of drinks per day using spaghetti and scatter plots. We will explore the association between baseline client characteristics on symptom trajectories. We will use survival analysis to calculate the number of sessions required for 25%, 50%, and 75% of clients to achieve one or two standard deviation(s) in symptom improvement from baseline. We will also calculate the percentage of clients that achieve these changes by the end of treatment. Collectively, these analyses will provide insight into *when* symptoms change over the course of treatment, which may be useful in refining CETA in future studies.

*Analysis of HIV outcome data.* In both RCT and non-RCT participants, we will use a linear model to investigate changes to MPR during the period before and after the intervention and a logistic model for changes to the proportion with HIV viral suppression (defined as <1000 copies/ml, the standard in SSA). We will compare visit adherence between those randomized to BI+CETA versus BI alone. Because of the relatively small sample sizes in this pilot study, these data will be primarily descriptive; however, these data will inform a follow-up grant.

*Analysis of uEtG results.* The purpose of uEtG testing is to confirm abstinence and not to validate AUDIT scores >0. Based on Preliminary Studies we expect to identify 'under-reporters,' defined as participants who report abstinence on AUDIT or TLFB and test uEtG-positive. In a secondary analysis, we will exclude under-reporters and re-assess the impact of the intervention on alcohol use and other outcomes.

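### Visit adherence is compared between arms with no planned baseline value, look-back window or baseline adjustment, at a modest cost in precision

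*Combined protocol and SAP*

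**What the plan says.** Four places in section V (Study Procedures, Study Implementation) bear on this.

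- *Stage 1B overview.* "Retention on ART and HIV viral suppression will also be assessed at baseline and 6-months post-baseline". The next paragraph promises before-and-after data for the cohort on the outcomes used in the RCT.
- *Baseline data collection.* Five items come from the clinic file: "These data are captured as part of HIV routine care in Zambia and include: (1) ART initiation date, (2) hepatitis B surface antigen", followed by the latest CD4+ count, cumulative and past 6-month MPR, and plasma viral load. Visit adherence is not among them.
- *Follow-up assessments.* The 6-month chart list is said to match the baseline one. Then, to supplement the MPR data on retention, "we will also assess visit adherence, the percentage of assigned pharmacy and clinical visits that were made", where a visit counts if the patient came within 3 days. No period is given over which visits are counted.
- *Analysis of HIV outcome data.* "We will compare visit adherence between those randomized to BI+CETA versus BI alone". No model, baseline term or change score is named. In the same paragraph, MPR and viral suppression are analysed as before/after changes with no arm term stated, and the HIV data are called primarily descriptive because the pilot is small.

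In section I, Hypothesis 2 under Aim 2 predicts better ART retention and viral load with BI+CETA than with BI alone, at p<.05.

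**The concern.** Visit adherence is introduced as a second measure of retention, and retention is meant to be assessed at both time points. As the plan stands, this measure has no pre-treatment value. Two things follow.

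- In the RCT, the arm comparison uses the 6-month value alone. Earlier attendance probably predicts later attendance. Randomisation is stratified by sex only, so earlier attendance is balanced by chance and not by design, and the variation it would explain stays in the error term.
- In the cohort, there is no before value, so the promised before-and-after estimate cannot be made for this outcome from the data the plan lists.

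The first point carries some weight because the HIV analysis paragraph attaches an explicit arm comparison to this outcome and to no other. The same paragraph says the HIV data will inform a follow-up grant. A baseline value would also supply the before/after correlation needed to plan that trial.

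**Working it through.** **The plan's own figure.** Section III.B sizes the RCT on AUDIT, with a standardised effect of 0.5, alpha 0.05 and 80% power: "we will require a total sample size of 128 (n=64 per arm"). A two-sided two-sample t-test gives 63.77, so 64 per arm and 128 in all. With 20% dropout, 128/(1 − 0.20) = 160: "we will inflate the sample size to 160 (n=80 per arm"). Both figures reproduce. They concern AUDIT and are not affected by this point. No sample size, SD or correlation is given for visit adherence.

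**Inputs for visit adherence.**

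- 64 analysed per arm, borrowed from section III.B.
- Outcome in SD units and treated as roughly normal (assumption; it is a bounded percentage).
- Correlation r between baseline and 6-month visit adherence of 0.3, 0.5 or 0.7 (assumption).

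**Formulas.** The unadjusted detectable effect at 80% power, from the t-test with 64 per arm, is 0.499 SD. The normal approximation (1.96 + 0.84) × √(2/64) gives 0.495. With the baseline value as a covariate, the residual SD is √(1 − r²). With a change score it is √(2(1 − r)). The detectable effect scales with the residual SD.

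| r | Variance ratio, covariate (1 − r²) | Detectable effect, covariate | Detectable effect, change score |
|---|---|---|---|
| 0.3 | 0.91 | 0.499 × 0.954 = 0.476 | 0.499 × 1.183 = 0.591 |
| 0.5 | 0.75 | 0.499 × 0.866 = 0.432 | 0.499 × 1.000 = 0.499 |
| 0.7 | 0.51 | 0.499 × 0.714 = 0.356 | 0.499 × 0.775 = 0.387 |

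The covariate therefore removes 9%, 25% or 49% of the variance. At r = 0.5 the gain equals 1/0.75 = 1.33, or 33% more participants. A change score is worse than the plain 6-month comparison when r is below 0.5, so a covariate is the safer use of the baseline value.

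**The same cost seen as imbalance.** The SD of the chance difference in baseline means is √(2/64) = 0.177 SD, a 95% range of about ±0.35 SD. At r = 0.5, about ±0.17 SD of that would pass into the unadjusted estimate. This restates the precision loss above and does not add to it.

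**If all 80 per arm have chart data.** The unadjusted detectable effect is about 0.45 SD. Multiplying by the same factors gives about 0.43, 0.39 and 0.32 SD. The proportional gain is unchanged.

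**The case against.** The case on the other side is substantial, and most of it stands.

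- *Not the only HIV comparison.* Hypothesis 2 states an arm comparison for ART retention and viral load. Visit adherence stands alone only within the HIV analysis paragraph.
- *Unplanned, not impossible.* A reader might infer that adjustment or a change score cannot be had. The documents do not support that. Follow-up assessments says all HIV data come from charts, so if the chart holds earlier visits, a pre-baseline value could be taken at the 6-month visit. There is a deadline, though. Section VI.d has identifying information destroyed after a participant's last visit, and section VII has the linking file destroyed at study end.
- *Inferred from omission.* No sentence confines visit adherence to 6 months, and the baseline list is introduced as what the data include. Even so, the follow-up text adds visit adherence separately, after saying the numbered items match baseline.
- *No bias.* Randomisation protects the 6-month comparison, and its confidence interval already allows for chance imbalance.
- *Low stakes.* The outcome supplements MPR, and the plan calls the HIV data primarily descriptive.
- *Comparator.* Past 6-month MPR is collected at baseline and is probably related to attendance. If the analysis adjusted for it, the further gain would be smaller than shown. The HIV analysis paragraph names no such adjustment, and the covariate rule elsewhere in the analysis plan is written for the ACASI outcomes.
- *Retrievability.* The documents imply but do not state that past assigned visits can be recovered from the file. Eligibility sets no minimum time on ART, so recent starters may have few earlier visits or none.

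**Conclusion.** The concern holds as a gap in specification. Visit adherence has no planned baseline value, look-back window or baseline adjustment, which sits poorly with the statement that retention is assessed at both times and with the promise of before-and-after data for the cohort.

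The cost in the RCT is precision. For r of 0.3 to 0.7 and 64 per arm, baseline adjustment would cut the variance by about 9% to 49% and bring the detectable effect from about 0.50 SD down to between 0.48 and 0.36 SD. These figures rest on an assumed correlation, approximate normality, and a comparison that uses no other baseline information.

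A reader might go further and conclude that the arm comparison is invalid or that Hypothesis 2 is left untestable. Neither follows: the randomised contrast is unbiased, and MPR and viral load, the measures behind Hypothesis 2, are extracted at both times. This is a worthwhile, inexpensive improvement to a supplementary outcome.

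**What to change.** - *Baseline data collection:* add visit adherence over the 6 months before baseline, using the definition in Follow-up assessments and the same window as past 6-month MPR. If time since ART start is shorter, count visits from ART start.
- *Follow-up assessments:* state the period over which 6-month visit adherence is counted.
- *Analysis of HIV outcome data:* compare 6-month visit adherence between arms with the baseline value as a covariate and not as a change score. For participants with no assigned visits before baseline, use a missing-baseline indicator. Use the same baseline value for the cohort's before-and-after estimate.
- *Timing:* confirm early that past assigned visits can be retrieved, and complete the extraction before the link between identity and study ID is destroyed.

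The cost is one more field from a file already being opened, and one covariate with its indicator. The downsides are a little extra extraction time and a noisy or absent baseline value for recent ART starters.
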